6.3 Excluded Medications

Corticosteroids and other immunosuppressive drugs should also be avoided for 3 months after CAR T cell administration, unless used to manage CAR T cell-related toxicities. Other medications that might interfere with the evaluation of the investigational product, such as non-steroidal anti-inflammatory agents should also be avoided for the same time period unless medically necessary. Physiologic steroids (less than or equal to 5mg/day) will be allowed on study.

Treatment for lymphoma such as chemotherapy, immunotherapy, targeted agents, radiation, and high dose corticosteroid, other than defined/allowed in this protocol, and other investigational agents are prohibited, except as needed for treatment of disease progression after the CAR T cell infusion and radiation therapy. Patients will be allowed to remain on maintenance therapy (ibrutinib, revlimid, etc) if these medications were initiated prior to and continued during CAR-T infusion.

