7.2 Adverse Events

An adverse event is defined as any untoward medical occurrence in a clinical trial subject. The event does not necessarily have a relationship to treatments provided leading to study eligibility. The investigator is responsible for ensuring that any adverse events observed by the investigator or reported by the subject are recorded in the subject's medical record.

The definition of adverse events includes worsening of a pre-existing medical condition. Worsening indicates that the pre-existing medical condition has increased in severity, frequency, and/or duration or has an association with a worse outcome. A pre-existing condition that has not worsened during the study or involves an intervention such as elective cosmetic surgery or a medical procedure while on study, is not considered an adverse event.

Interventions for pretreatment conditions (such as elective cosmetic surgery) or medical procedures that were planned before study participation are not considered adverse events. Hospitalization for study treatment infusions or precautionary measures per institutional policy are not considered adverse events.

The term “disease progression” as assessed by measurement of malignant lesions on radiographs or other methods should not be reported as adverse events. Death due to disease progression in the absence of signs and symptoms should be reported as the primary tumor type (e.g., B-Cell Lymphoma).

For situations when an adverse event or serious adverse event is due to the disease under investigation report the signs and symptoms. Worsening of signs and symptoms of the malignancy under study should also be reported as adverse events in the appropriate section of the CRF.

The investigators clinical judgment is used to determine whether a subject is to be removed from treatment due to an adverse event. In the event a subject request to withdraw from protocol required therapies or the study due to an adverse event, the subject should undergo the procedures outlined in the Month 3 visit of the SOA.

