7.4 Procedures for AE and SAE Collection and Reporting

7.4.1 Reporting of Adverse Events

The investigator is responsible for ensuring that all adverse events observed by the investigator or reported by the subject that occur from enrollment (ie, radiation therapy consultation) through 3 months after RT are monitored and reported. After 3 months, targeted adverse events including (eg, neurological, hematological, infections, autoimmune disorders, and secondary malignancies) will be monitored and reported for 6 months after treatment with axicel or tisacel or until disease progression, whichever occurs first.

The investigator must address the below for adverse events:

- Adverse event diagnosis or syndrome (if not known, signs or symptoms)
- Dates of onset and resolution
- Severity
- Assessment of relatedness to investigational product, lymphodepleting chemotherapy or study procedures
- Action taken

In reviewing adverse events, investigators must assess whether the adverse event is possibly related to 1) CAR T cell therapy product 2) RT, or 3) any protocol-required study procedure. The relationship is indicated by a yes or no response and entered into the CRF. A yes response should indicate that there is evidence to suggest a causal relationship between the study treatment or procedure and the adverse event. Additional relevant data with respect to describing the adverse event will be collected in the CRFs.

The investigator is responsible for reviewing laboratory test results and determining whether an abnormal value in an individual study subject represents a clinically significant change from the subject's baseline values. In general, abnormal laboratory findings without clinical significance (based on the Investigator's judgment) are not to be recorded as adverse events. However, abnormal laboratory findings that result in new or worsening clinical sequelae, require therapy or adjustment in current therapy are considered adverse events. Where applicable, clinical sequelae (not the laboratory abnormality) are to be recorded as the adverse event.

The investigator is expected to follow reported adverse events until stabilization or resolution. If a subject begins a new anticancer therapy, the adverse event reporting period for non-serious adverse events ends at the time the new treatment is started.

7.4.2 Reporting of Serious Adverse Events and Non-serious CRS events Grade ≥ 3

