The investigator is responsible for reporting all serious adverse events observed by the investigator or reported by the subject that occur after signing of the consent through 3 months after the RT. After 3 months, only serious targeted adverse events (e.g., neurological, hematological, infections, autoimmune disorders, and secondary malignancies) observed by the investigator or reported by the subject will be reported for 6 months after RT or until disease progression, whichever occurs first. For subjects who screen fail or are enrolled but do not receive RT, the reporting period for serious adverse events ends 30 days after the last procedure (e.g., biopsy).

Serious events that the investigator assesses as related to RT should be reported regardless of the study period.

All serious adverse events and non-serious CRS events \geq Grade 3 ²² must be submitted within 24 hours following the investigators knowledge of the event **using a SAE Report Form. Refer to the SAE Report Form for instructions on how to submit the SAE report.** Subsequently, all serious adverse events will be reported to the health authorities per local reporting guidelines.

Progression of the malignancy during the study should not be reported as a serious adverse event. Adverse events associated with disease progression may be reported as serious adverse event. If the malignancy has a fatal outcome within 3 months of the last day of the lymphodepleting therapy,

CAR T infusion, or RT, then the event leading to death must be recorded as a serious adverse event with CTCAE Grade 5.

Death must be reported if it occurs during the serious adverse event reporting period, irrespective of any intervening treatment.

Any death occurring after the first dose of chemotherapy, for the purpose of pre-lymphodepletion, and within 3 months of the CAR T infusion or RT, regardless of attribution to treatment, requires expedited reporting within 24 hours. Any death occurring greater than 3 months after the CAR T infusion or RT requires expedited reporting within 24 hours only if it is considered related to treatment.

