12.1 Study Endpoints

Primary Endpoint:

- Rate and severity of RT-related toxicity as per CTCAE v5.0 criteria during RT or within the first 30 days of completing RT.

Secondary Endpoints:

- **Duration of response (DOR):** Among subjects who experience an objective response, DOR is defined as the date of their first objective response (which is subsequently confirmed) to disease progression per Lugano criteria¹ or death regardless of cause. Subjects not meeting the criteria for progression or death by the analysis data cutoff date will be censored at their last evaluable disease assessment date and their response will be noted as ongoing.
- **Objective response rate (ORR) per IRRC:** ORR per IRRC is defined as the incidence of either a complete response or a partial response by Lugano criteria¹ as determined by the IRRC. All subjects that do not meet the criteria for an objective response by the analysis data cutoff date will be considered non-responders.
- **Progression-free Survival (PFS):** PFS is defined as the time from RT completion date to the date of disease progression per Lugano criteria¹ or death from any cause. Subjects not meeting the criteria for progression by the analysis data cutoff date will be censored at their last evaluable disease assessment date.

- **Overall survival (OS):** OS is defined as the time from RT completion to the date of death. Subjects who have not died by the analysis data cutoff date will be censored at their last contact date.

Exploratory Endpoints:

- Levels of anti-CD19 CAR T cells in blood
- Levels of cytokines in serum
- Incidence of anti-axicabtagene ciloleucel antibodies
- Investigation of potential biomarker development based on assessment of blood cells, tumor cells and the proposed actions of the investigational product.

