12.3 Interim Monitoring Plan

Interim Analysis and Early Stopping Rules

The SRT will review safety data when 3 and 10 subjects treated have had the opportunity to be followed for 30 days, respectively. The study will be stopped if any patients develop grade 4 or higher toxicity attributed to RT rather than to lymphoma progression or other cause as per SRT.

Safety Interim Analysis

The SRT will review AE and SAE information on a regular basis throughout subject treatment in Phase 2 of the study. The SRT may request additional safety data or modifying the study conduct. The sponsor may request additional reviews by the SRT if safety concerns are identified. Data submitted to the SRT may be monitored or unmonitored to facilitate timely review.

Efficacy Interim Analysis

There is no planned efficacy interim analysis for this portion of the study.

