12.4 Analysis of Primary and Secondary Endpoints

Planned Method of Analysis

The primary analysis of all treated subjects will take place once they have had the opportunity to be followed for 6 months.

Descriptive analyses may occur at any time.

Objective Response Rate

The incidence of objective response and exact 2-sided 95% confidence intervals will be generated.

Duration of Response

The competing-risk analysis method ^{24,25} will be used to estimate the cumulative incidence of relapse. The cumulative incidence of relapse in the presence of non-disease related mortality (the competing risk) will be estimated along with 2-sided 95% confidence intervals at 3-month intervals.

Progression-free Survival

Kaplan-Meier estimates and 2-sided 95% confidence intervals will be generated for progression-free survival time. Estimates of the proportion of subjects alive and progression-free at 3-month intervals will be provided.

Overall Survival

Kaplan-Meier estimates and 2-sided 95% confidence intervals will be generated for OS. Estimates of the proportion of subjects alive at 3-month intervals will be provided.

Safety

Subject incidence rates of adverse events including all, serious, fatal, CTCAE version 5.0 Grade 3 or higher and treatment related AEs reported throughout the conduct of the study will be tabulated by preferred term and system organ class. Changes in laboratory values and vital signs will be summarized with descriptive statistics. The incidence of concomitant medications will be summarized.

Tables and/or narratives of deaths through the long-term follow-up and treatment related SAEs will be provided.

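### Non-serious AE reporting ends at a new anticancer therapy with no exemption for the 30-day primary toxicity window; the end dates for late targeted AEs also disagree

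*Combined protocol and SAP*

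**What the plan says.** **Endpoint.** Section 12.1 defines the primary endpoint as "Rate and severity of RT-related toxicity as per CTCAE v5.0 criteria during RT or within the first 30 days of completing RT". It is not limited to serious events.

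**Reporting period.** Section 7.4.1 collects all AEs from enrollment to 3 months after RT. It then adds that, for a subject who begins a new anticancer therapy, "the adverse event reporting period for non-serious adverse events ends at the time the new treatment is started".

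**New therapy.** Section 6.3 bars other lymphoma treatment "except as needed for treatment of disease progression after the CAR T cell infusion and radiation therapy" and states no waiting period. Section 6.4 records subsequent therapy.

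**Progression path.** Under Section 9.7.4, a subject who progresses in the post-RT period and is not re-treated goes straight to a Month 3 visit, then into follow-up for survival, later therapy and disease outcome. Table 2 ends at Week 4 after RT and Table 3 has Months 6, 9 and 12. Neither has a Month 3 column.

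**Passages that pull the other way.** Table 2 marks AE collection at every visit through Week 4, and Section 7.9 wants every AE in routine submissions. Neither mentions new therapy.

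**Safeguards.** On events already reported, Section 7.4.1 says: "The investigator is expected to follow reported adverse events until stabilization or resolution". Section 7.2 requires that "any adverse events observed by the investigator or reported by the subject are recorded" in the medical record. Section 7.4.2 adds: "Serious events that the investigator assesses as related to RT should be reported regardless of the study period". Table 2 also places a CTCAE/PRO-CTCAE survey at Week 1 after treatment.

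**Late targeted AEs.** The stated end is 6 months after axicel or tisacel (7.4.1), 6 months after RT for serious events (7.4.2), or 24 months for AEs and SAEs alike (Table 3, footnote 7). The last scheduled visit is Month 12 (9.7.5).

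**The concern.** The safety of RT is the primary objective. A collection rule that can close before the primary window does may remove events from the endpoint itself. The cut-off is also unlikely to fall at random, because the permitted reason for new therapy is progression.

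The RT risks named in Section 7.1 (dermatitis, pneumonitis, esophagitis, fatigue) can all occur in non-serious form, which is the form exposed to the cut-off. The result is to be set against historical controls (Section 12.5) and used to design a larger study (Section 12.2), so an under-count would carry forward.

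For late events, the text does not tell site staff when targeted collection stops.

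**Working it through.** The plan gives no figure for early switching or for the RT toxicity rate, so there is no stated result to reproduce. The check is a comparison of passages, followed by an illustration on assumed inputs.

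**1. Do the windows overlap?** The endpoint window runs from the start of RT to 30 days after its end. The cut-off applies from the start of new therapy. Section 6.3 allows that therapy for progression after CAR-T and RT, so the exposed part is mainly the 30 days after RT. Section 7.4.1 is the only passage that says what a switch does to non-serious reporting, and it ends it. The exception for RT-related events in 7.4.2 is limited to serious ones. Table 2 and Section 7.9 conflict with the cut-off but do not override it, and Section 9.7.4 may take the likely switchers off the weekly schedule. What is exposed is therefore non-serious RT-related toxicity whose onset follows a switch inside the window.

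**2. How large could it be?** Let p be the true share of patients with RT toxicity and s the share who switch inside the window. Let h be the share of switchers with toxicity whose RT toxicities are all non-serious and all begin after the switch. If switching is independent of toxicity and cut-off patients count as event-free:

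recorded rate = p × (1 − s × h)

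With p = 0.5 and h = 0.5 (both assumed) and the planned 20 patients:

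| s | recorded rate | patients of 20 |
|---|---|---|
| 0% | 50% | 10 |
| 5% | 0.5 × (1 − 0.025) = 48.75% | 9.75 |
| 10% | 0.5 × (1 − 0.05) = 47.5% | 9.5 |
| 20% | 0.5 × (1 − 0.10) = 45% | 9 |

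Over s = 5% to 20% and h = 0.25 to 0.75, the relative loss s × h runs from 0.05 × 0.25 = 1.25% to 0.20 × 0.75 = 15%. In patients, 20 × 0.5 × s × h runs from 0.125 to 1.5.

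h falls when patients have several toxicities. If each begins after the switch with probability 0.5 independently, h = 0.5, 0.25 and 0.125 for one, two and three toxicities. At s = 10% the recorded rates are then 47.5%, 48.75% and 49.4%. For scale, the exact 95% interval for 10 of 20 is 27.2% to 72.8%.

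This covers only the any-toxicity patient rate. Severity and the counts by preferred term (Section 12.4) can also lose events in patients already counted.

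**3. Does the direction depend on handling?** Yes. Suppose instead that switchers with no recorded event are dropped from the denominator. At p = 0.5, s = 0.10, h = 0.5 the dropped share is 0.10 × (0.5 + 0.5 × 0.5) = 0.075. The rate becomes 0.475 / 0.925 = 51.4%, slightly above the truth. The plan does not say which rule applies.

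**4. Late targeted AEs.** Take RT ending on day 44 after infusion (refractory at day 30, 7 days of planning, an assumed 7-day course) and 6 months = 183 days. Section 7.4.1 then ends at day 183 and Section 7.4.2 at day 44 + 183 = 227. Footnote 7 ends at 24 months, which is 12 months beyond the last scheduled visit. The footnote states no anchor, although Table 3 counts visits from infusion. The anchor in 7.4.1 names two products, while any CD19-targeted product is eligible.

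**The case against.** The strongest reply is that the effect is small and no decision depends on it. Switching may be rare: no PET is scheduled between RT and Month 6 after infusion, so earlier progression is found mainly through symptoms (Section 10.1). The illustrated loss at 10% switching is far inside sampling error, and there is no hypothesis test. Attribution to RT is also harder once systemic therapy has begun, so open collection may add misattributed events. All of this stands. It limits the weight of the point, but it does not justify leaving the primary window open to a cut-off.

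A reader might infer four stronger things that the documents do not support.

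- **That the stopping rule is undermined.** Section 12.3 says "The study will be stopped if any patients develop grade 4 or higher toxicity attributed to RT". Life-threatening and other medically important events are serious (7.2.1), and RT-related serious events stay reportable in any period. Only a grade 4 event not classed as serious could slip through.
- **That the rate must be biased downward.** Section 12.4 says "The primary analysis of all treated subjects will take place once they have had the opportunity to be followed for 6 months". That fixes the timing of the analysis, not the handling of incomplete windows.
- **That all information after a switch is lost.** Events already reported are followed, observed events go in the medical record, and the Week 1 survey gives one capture point inside the window.
- **That the late targeted window in 7.4.1 is empty for some patients and so loses data.** If RT ends on day 98, 3 months later (91 days) is day 189, past day 183. But 7.4.1 already collects all AEs up to that point, so nothing within 6 months of infusion is lost.

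Sections 7.4.1 and 7.4.2 might also differ by design, one covering targeted AEs in general and the other serious ones. Footnote 7 covers both and matches neither.

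**Conclusion.** The point holds as a gap in data collection for the primary endpoint. Followed as written, Section 7.4.1 allows non-serious RT-related toxicity with onset after an early switch to go unreported inside the endpoint window, and Section 9.7.4 may remove the same subjects from weekly checks. If they are then counted as event-free, the primary rate is under-counted.

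The size cannot be derived from the documents and may be zero. The 0.1 to 1.5 of 20 patients rests on assumed values for the true rate, the switching share and the share missed, and on switching being independent of toxicity. The grade 4 or higher stopping rule is largely unaffected. This should be corrected because it touches the primary endpoint and is cheap to close, not because a large bias has been shown.

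The contradictory end dates for late targeted AEs are a separate defect in the text and rest on no assumed rate.

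**What to change.** 1. In Section 7.4.1, state that all AEs, serious or not, are collected through at least 30 days after RT completion, regardless of progression or new anticancer therapy.
2. Align the progression path in Section 9.7.4 with this. Changing 7.4.1 alone would leave the two in conflict. Scheduled visits, record review or telephone contact can supply the data, so no new visit type is needed. Resolve the reference to a Month 3 visit that neither table contains.
3. Use the new-therapy start date, available from the records under Section 6.4, to show events with onset after a switch separately.
4. In Section 12.4, state how patients with an incompletely observed window enter the denominator, with a best-case and worst-case bound. For example, with 6 of 20 recorded and 4 cut-off patients without a recorded event, the bounds are 6/20 = 30% and 10/20 = 50%.
5. Separately, reconcile the targeted-AE end dates in 7.4.1, 7.4.2 and Table 3 footnote 7 to one anchor and one end date, and say how events are collected if that date falls after Month 12.

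The cost is a few sentences, some extra AE entries and some contact with subjects who have left the weekly schedule. The downside is weaker attribution to RT after a switch, which is why those onsets need the flag.

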7.4.3 Pregnancy and Lactation

There is no relevant clinical experience with CAR T cell therapy in pregnant or lactating women, and animal reproductive studies have not been performed. Women of childbearing potential must have a negative pregnancy test prior to enrollment because of the potentially dangerous effects of the RT on the fetus. RT should not be administered to pregnant women.

If a pregnancy occurs in a female subject enrolled into the study, or a female partner of a male subject, within 6 months of completing RT, the pregnancy must be reported to the PI. Information regarding the pregnancy and/or the outcome may be requested by the PI.

In addition to reporting any pregnancies occurring during the study, investigators should monitor for pregnancies that occur after the last dose of axicel or tisacel through 6 months for female subjects and for 6 months for the female partner of the male subjects.

The pregnancy should be reported to the PI contact within 24 hours of the investigator knowledge of the pregnancy event.

7.4.4 Criteria to Pause Enrollment

Enrollment will be paused if any of the following criteria is met:

- 1) Any subject with grade 4+ RT-related adverse events
or
- 2) Subject incidence of the following Grade 4+ CAR-T-related adverse events lasting more than 7 days is > 33%:
 - Neurologic toxicities
 - CRS (per ASTCT 2019)
 - Other non-hematological serious adverse event
 - Infection (treatment-related)

DF/HCC Adverse Event Reporting Guidelines

Investigative sites within DF/HCC will report AEs directly to the DFCI Office for Human Research Studies (OHRS) per the DFCI IRB reporting policy.

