7. ADVERSE EVENTS: LIST AND REPORTING REQUIREMENTS

7.1 Expected Toxicities

To date, the following important risks have been identified with axicel and tisacel: CRS, neurologic toxicities, infections, and cytopenias. Grading and management of these toxicities will be performed utilizing the recently released ASTCT CRS/ICANS grading system²¹. Please refer to the current product label for axicel, tisacel, lisocabtagene maraleucel, and brexucabtagene autoleucel for discussion of CRS and neurotoxicity (ICANS). Treatment with RT will occur after 30 day post-infusion period during which centers are FDA mandated to observe for peak toxicities. Additional information and management recommendations can also be found in appendix A. The following are important risks identified with radiation therapy but depend upon the target site for radiation therapy: dermatitis, pneumonitis, esophagitis, fatigue.

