7.3 Adverse Event Characteristics

Adverse Event Assessment

For all AEs, the Investigator must determine both the severity of the AE and the relationship of the AE to CAR T cells treatment. Additionally, patients will also self-report adverse event outcomes pertaining to the region of interest as per their RT treatment field.

- **CTCAE term (AE description) and grade:** All non-CRS/ICANS toxicities will be graded

per CTCAE by the Investigator. The descriptions and grading scales found in the revised NCI Common Terminology Criteria for Adverse Events (CTCAE) version 5.0 will be utilized for AE reporting. All appropriate treatment areas should have access to a copy of the CTCAE version 5.0. A copy of the CTCAE version 5.0 can be downloaded from the CTEP web site:

http://ctep.cancer.gov/protocolDevelopment/electronic_applications/ctc.htm

- **PRO-CTCAE** – Patients will also have the opportunity to self-report adverse event outcomes. The descriptions and grading scales found in the NCI Patient Reported Outcomes Common Terminology Criteria for Adverse Events (PRO-CTCAE) version 1.0 will be utilized. A copy of the possible items for PRO-CTCAE will can be downloaded from the NCI website. Patient will be asked to fill out the applicable section of the survey depending on their radiation treatment site, including items for pain and mood for all patients:
<https://healthcaresdelivery.cancer.gov/pro-ctcae/instrument.html>
- **ASTCT CRS/ICANS:** Any delayed CAR-T related CRS and/or neurotoxicity (ICANS) will be graded using the ASTCT 2019 CRS/ICANS grading system (appendix A).
- **For expedited reporting purposes only:**
 - AEs for agents utilized in this study should be reported only if the adverse event varies in nature, intensity or frequency from the expected toxicity information which is provided.
 - Other AEs for the protocol that do not require reporting are outlined in the next section (Expedited Adverse Event Reporting) and under the sub-heading of Protocol-Specific Expedited Adverse Event Exclusions.
- **Attribution** of the AE:
 - Definite – The AE *is clearly related* to the study treatment.
 - Probable – The AE *is likely related* to the study treatment.
 - Possible – The AE *may be related* to the study treatment.
 - Unlikely – The AE *is doubtfully related* to the study treatment.
 - Unrelated – The AE *is clearly NOT related* to the study treatment.

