11.2 Data Safety Monitoring

The DF/HCC Data and Safety Monitoring Committee (DSMC) will review and monitor toxicity and accrual data from this study. The committee is composed of medical oncologists, research nurses, pharmacists and biostatisticians with direct experience in cancer clinical research. Information that raises any questions about participant safety will be addressed with the Overall PI and study team. In addition to the DF/HCC DSMC, a safety review team (SRT) comprised of the study sponsor and Kite/Gilead, will review the safety data and make recommendations on further study conduct as described below.

The DSMC will review each protocol up to four times a year with the frequency determined by

the outcome of previous reviews. Information to be provided to the committee may include: up-to-date participant accrual; current dose level information; DLT information; all grade 2 or higher unexpected adverse events that have been reported; summary of all deaths occurring within 30 days of intervention for Phase I or II protocols; for gene therapy protocols, summary of all deaths while being treated and during active follow-up; any response information; audit results, and a summary provided by the study team. Other information (e.g. scans, laboratory values) will be provided upon request.

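### Read literally, pause criterion 2 in section 7.4.4 leaves out a CAR-T-related event that is fatal within 7 days and judged unrelated to RT, though it counts a non-fatal Grade 4 event lasting 8 days

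*Combined protocol and SAP*

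**What the plan says.** Section 7.4.4 gives two criteria, either of which pauses enrollment. Criterion 1 is met by a single subject with an RT-related event of grade 4 or higher and has no duration condition. Criterion 2 is met when "Subject incidence of the following Grade 4+ CAR-T-related adverse events lasting more than 7 days is > 33" percent, for neurologic toxicity, CRS, other non-hematological serious events and treatment-related infection.

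The only other automatic rule is in section 12.3: "The study will be stopped if any patients develop grade 4 or higher toxicity attributed to RT". It is likewise confined to RT.

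Several other provisions bear on the point:

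- **Timing (7.1).** "Treatment with RT will occur after 30 day post-infusion period during which centers are FDA mandated to observe for peak toxicities".
- **Delayed toxicity (7.3).** It is foreseen: "Any delayed CAR-T related CRS and/or neurotoxicity (ICANS) will be graded using the ASTCT 2019 CRS/ICANS grading system".
- **Attribution (7.4.1).** "investigators must assess whether the adverse event is possibly related to 1) CAR T cell therapy product 2) RT", with study procedures as a third item and a yes/no answer for the CRF.
- **Event dates (7.4.1).** Investigators record "Dates of onset and resolution". No convention is given for an event that ends in death.
- **Death reporting (7.4.2).** A death "within 3 months of the CAR T infusion or RT, regardless of attribution to treatment, requires expedited reporting within 24 hours". Later deaths get expedited reporting if considered treatment-related.
- **Oversight (11.2, 12.3).** "The DSMC will review each protocol up to four times a year". The safety review team (SRT) looks at safety data at 3 and 10 treated subjects and regularly in between, and may ask for changes to study conduct.

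**The concern.** A duration condition is a sensible filter for Grade 4 events, because it separates a brief, reversible episode from a prolonged one. Applied to a fatal event it works backwards: the faster the death, the less likely it is to count. A safety rule should not rank a death on day 3 below a survivable event that lasts 8 days.

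The case is worth settling because criterion 2 is the only automatic rule for toxicity attributed to the CAR T product and not to RT. Safety is the primary objective, and the stated rationale (section 3.2.1) is that RT may act together with CAR T cells that are still active. If the rule omits the death, any pause depends on the judgment of the SRT or the data and safety monitoring committee (DSMC).

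**Working it through.** The protocol gives no derivation for the 33% or 7-day limits, so there is no plan figure to reproduce. The check has two parts.

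**1. Which rule catches which event.** Take a listed CAR-T-related event and read the text literally.

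| Event | Criterion 1 | Criterion 2 | 12.3 stopping rule |
|---|---|---|---|
| Non-fatal Grade 4, 8 days, not RT-related | no | counts | no |
| Fatal after more than 7 days, not RT-related | no | counts | no |
| Fatal within 7 days, not RT-related | no | **does not count** | no |
| Fatal within 7 days, also judged RT-related | pauses | does not count | applies if the SRT attributes it to RT |

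Only the third row is a gap. Because 7.4.1 asks about CAR T and RT separately, a yes for the first and a no for the second is a recordable outcome.

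**2. What one omitted death does to the count.** Let n be the denominator and x the number of subjects who count. The rule fires at the smallest x with x/n above the threshold. The printed figure can mean 0.33 or one third, so both are shown.

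| n | x needed (0.33) | x needed (one third) | One short |
|---|---|---|---|
| 1 | 1 (1/1 = 100%) | 1 | 0 |
| 2 | 1 (1/2 = 50%) | 1 | 0 |
| 3 | 1 (1/3 = 33.3%) | 2 (2/3 = 66.7%) | 0 or 1 |
| 4 | 2 (2/4 = 50%) | 2 | 1 (25%) |
| 10 | 4 (4/10 = 40%) | 4 | 3 (30%) |
| 20 | 7 (7/20 = 35%) | 7 | 6 (30%) |

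An omitted death changes the outcome only if the other counted subjects are exactly one short of x:

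- **n = 3, threshold 0.33:** with no other event, 0/3 = 0% as written and 1/3 = 33.3% if counted. The pause turns on the death alone.
- **n = 3, threshold one third:** with exactly one other subject counting, 1/3 = 33.3% as written (no pause) and 2/3 = 66.7% if counted.
- **n = 10:** with exactly 3 others, 30% as written and 40% if counted.
- **n = 20:** with exactly 6 others, 30% as written and 35% if counted.

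So one death is decisive alone at n of 3 or fewer (0.33) or 2 or fewer (one third). The numbers of other events are chosen to show where the result flips; they are not forecasts.

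**The case against.** The strongest reply is that the gap exists on only one reading. Events are dated by onset and resolution, a fatal event has no resolution, and so it can be said to outlast any 7-day limit. The words Grade 4+ also suggest that deaths were meant to be included. This is a reasonable reading, but the protocol does not adopt it, and a site could equally end the event at the date of death.

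The second reply is that little is left to fall through. RT starts after the 30-day observation period, which leaves delayed CRS or ICANS and later infections or other serious events. In a study built on synergy between RT and CAR T, a sudden death after RT may well be judged related to both, and criterion 1 then applies. The death would be reported within 24 hours and would reach the SRT. Leaving one unusual death to expert review is defensible in a 20-patient pilot. All of this stands. It limits how often the gap could matter and does not correct the wording.

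Third, the 33% threshold governs the rule more than the 7-day phrase does. Even after rewording, 3 deaths in 10 or 6 in 20 would not pause enrollment under criterion 2. That is true; the rewording corrects the ranking of events, not the leniency of the threshold.

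A reader might also infer that the omission would change the outcome of the SRT review at 3 subjects. The documents do not support that: 7.4.4 gives no checking time and no denominator, and 12.3 does not link its reviews to criterion 2.

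**Conclusion.** The concern holds as a narrow wording fault of low severity. It rests on three conditions: the event is CAR-T-related and of a listed type, it is fatal within 7 days of onset and judged unrelated to RT, and a fatal event is not treated as unresolved. Under those conditions the stated rule counts a less serious event and omits a more serious one, and no other automatic rule makes up for it.

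The numerical effect is small except at very small denominators, as the table shows. No probability can be attached, because the documents give no rate for such events and leave open when, and on what denominator, the criterion is evaluated.

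Two stronger readings should be resisted. The rule does not ignore all CAR-T-related deaths: those following an event of more than 7 days count. Nor would a rapid death go unseen, since reporting and review still apply. The primary endpoint, sample size and analysis are unaffected.

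**What to change.** Reword criterion 2 to: *the proportion of treated subjects with a CAR-T-related event of the following types that is fatal (any duration) or Grade 4 lasting more than 7 days is > 33%*.

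Use the word fatal, not Grade 5. Section 7.3 grades CRS and ICANS by the ASTCT system, and the tables in Appendix A stop at Grade 4, so a reference to Grade 5 could leave a fatal CRS or ICANS event in doubt.

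The new wording also names a denominator. Two short additions would help but are optional: when the criterion is checked (the 12.3 reviews are one choice), and whether 1 of 3 subjects is enough to trigger it.

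The cost is one line of protocol text, with no change to sample size, visits or data collection. If the sponsor already meant that a fatal event never resolves, the line simply confirms it.
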